Blood samples will be collected in both cohorts for PK parameter analysis, plasma oxalate sample analysis, and to establish plasma oxalate profiles (in Cohort B only; the profile enables AUC calculation between dialysis sessions) (Table 5, Table 6). From Screening to Day 1, patients will have at least 4 plasma oxalate collections (pre-dialysis in Cohort B) to establish a robust baseline measurement. The plasma oxalate sample collection during Screening is described per cohort in Figure 1, and during the treatment period will be performed as per the Schedules of Assessments (see Table 1, Table 2, Table 3, and Table 4).

Patients who are anuric are defined as producing <100 ml of urine per day. For all patients who are not anuric (ie, can produce \geq 100 ml of urine per day), single-void urine samples (in triplicate) will be collected during screening to establish baseline and then serially per the Schedules of Assessments.

For patients able to provide 24-hour urine samples, three 24-hour urine collections will be scheduled during screening to establish baseline urinary oxalate levels. At Month 6, three 24-hour urine collections will be scheduled within 14 days prior to dose. There will be a single 24-hour urine collection at Month 3, Month 12, and every 6 months thereafter while on study.

This study will consist of 2 periods: a 6-month primary analysis period followed by a long-term extension period. During the 6-month primary analysis period, patients will undergo efficacy and safety assessments every 2 weeks for the first month and monthly thereafter. During the long-term extension period of up to 54 months, dosing will continue and visits will occur at least every-3-months.

Patients who discontinue study drug early will be asked to return for follow-up visits as described in Section 4.3.1.

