6.2.2. Urinary Oxalate

In patients in both Cohort A and Cohort B who are not anuric (ie, patients who are able to continue to produce urine ≥ 100 ml per day) and are able to complete the collection procedure, 24-hour urinary oxalate excretion will be assessed. Since not all patients will be able to provide 24-hour urine samples, single-void urine samples (in triplicate) will be collected throughout the study in all patients who are not anuric. Table 12 shows the 24-hour urine collection procedure by study visit.

In patients who are able to comply with 24-hour urine collection procedures, urinary oxalate excretion will be determined from 24-hour urine sample collections to be completed at the time points specified in the Schedules of Assessment (see Table 1, Table 2, Table 3, and Table 4). Urinary oxalate concentrations will be analyzed centrally using a validated assay. 24-hour urine collections in patients not undergoing dialysis must meet pre-specified validity criteria (see Section 6.2.2.1).

For patients who are able to comply with the 24-hour urine collection procedure, three 24-hour urine collections will be scheduled during screening to establish baseline urinary oxalate excretion. For Month 6, three 24-hour urine collections will be scheduled within 14 days prior to dose to evaluate changes in oxalate concentrations over the 6-month interval. A single 24-hour collection will be scheduled at Month 3, Month 12, and then every 6 months thereafter as specified in the Schedules of Assessments (see Table 1, Table 2, Table 3, and Table 4). In patients undergoing dialysis, the timing of the collections relative to patients' weekly dialysis schedule should remain consistent for each patient, when possible.

Patients able to comply with 24-hour urine collections will either bring a 24-hour urine collection to the clinic, courier samples to the laboratory, or have their 24-hour urine collected during an inpatient stay at the time of the study visit.

All patients who are not anuric will have 3 single-void urine samples collected during Screening (first morning voids are preferred, when feasible). Following screening, single-void collections are performed within 7 days predose, as specified in the Schedules of Assessment (see Table 1, Table 2, Table 3, and Table 4). Samples may be collected as an outpatient prior to the visit or collected during the study visit prior to dosing, as applicable.

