AUC(0-24h) will be calculated using plasma oxalate results with the linear-trapezoidal method using actual collection times relative to pre-dialysis sampling time. An exact 24h assessment for the purpose of calculating the AUC(0-24h) will be calculated using linear interpolation or extrapolation on the two non-missing scheduled assessments closest to the 24-hour timepoint.

Plasma oxalate profiles will be compared across visits within patients. LS mean percent change from baseline plasma oxalate AUC(0-24h) at Month 6 and its associated 95% confidence interval will be estimated using MMRM model including data evaluated at Month 3 and Month 6. Additionally, the AUC(0-24h) parameter will be listed and descriptively summarized by study visit. The Full Analysis Set will be used for this analysis. A similar approach as used for the primary analysis will apply, in case when the model fails to converge.

Additionally, AUC(4-24h) will be similarly analyzed. AUC(4-24h) is defined as the plasma oxalate area under the curve of the 20 hour window from the end of dialysis (30 minutes before the end of dialysis assessment) until the next dialysis session (24h timepoint). This approach is intended to reduce the variability introduced by different dialysis parameters between patients. The percent change from baseline in plasma oxalate AUC(4-24h) will be summarized through Month 6 in a similar manner to the percent change from baseline in plasma oxalate AUC(0-24h) as a sensitivity analysis to the secondary endpoint. The pre-dialysis scheduled assessment will not be required for a valid AUC or utilized in this assessment, otherwise this analysis will remain consistent with methodology to assess the percent change from baseline in plasma oxalate AUC(0-24h).

7.3.2. Change from baseline to Month 6 in other Plasma and Urinary Oxalate Parameters

The analyses for the following secondary endpoints will also be performed using a restricted maximum likelihood based Mixed-effect Model Repeated Measures approach.

- Absolute change from baseline to Month 6 in plasma oxalate during the Primary Analysis Period
- Percent change and absolute change from baseline to Month 6 in 24-hr urinary oxalate corrected for BSA during the Primary Analysis Period
- Percent change and absolute change in spot urinary oxalate: creatinine ratio during the Primary Analysis Period

[figure not shown]

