Analysis by cohort will include evaluable assessments through Month 6, which will be modeled with fixed effects of scheduled visits and baseline covariate of corresponding assessment,

including patient as a random factor. LS mean of an endpoint of Month 3 to Month 6, averaged over these timepoints will be presented along with corresponding SEMs and 95% CIs. The autoregressive (1) covariance structure matrix will be used to model the within-patient error given the small sample size for this study. Similar approach as used for the primary analysis will apply, in case when the model fails to converge.

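### SAP 7.3.2 gives 24-hour urinary oxalate three covariance parameters where two visits identify two quantities; AUC has the same fault if the same model is meant, and its fallback does not fix the time point

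*SAP*

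**What the plan says.** SAP 7.3.2 analyses absolute change in plasma oxalate, 24-hour urinary oxalate corrected for BSA, and the spot oxalate:creatinine ratio with a REML mixed model. Visit and baseline are fixed effects, "including patient as a random factor", and for the residual: "The autoregressive (1) covariance structure matrix will be used to model the within-patient error given the small sample size for this study". The reported quantity is the LS mean averaged over Month 3 to Month 6.

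The 24-hour urine schedule is in Protocol 6.2.2: "A single 24-hour collection will be scheduled at Month 3, Month 12, and then every 6 months thereafter". At the later visit: "For Month 6, three 24-hour urine collections will be scheduled within 14 days prior to dose". SAP 5.2 reduces repeated collections at a visit to their mean unless otherwise noted, so each patient contributes two post-baseline values through Month 6.

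For AUC(0-24h) in Cohort B, SAP 7.3.1 reports the LS mean percent change at Month 6, "estimated using MMRM model including data evaluated at Month 3 and Month 6". It names neither a random patient term nor a residual structure. AUC(4-24h) follows the same method. On failure, 7.3.1 says: "A similar approach as used for the primary analysis will apply, in case when the model fails to converge". In SAP 7.1 that approach is an ANCOVA of the Month 3 to Month 6 average, used when the AR(1) fit does not converge.

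**The concern.** The model has a patient variance, a residual variance and a correlation. With two visits, the patient variance and the AR(1) correlation both act through the single covariance between those visits, so the data cannot separate them. Many parameter sets fit equally well and the information matrix is singular.

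Two consequences matter. First, the switch to ANCOVA depends on whether the model converges, yet the SAP does not say how to class a fit that stops on a flat likelihood with a singular Hessian. Second, the AUC result is fixed at Month 6 while the fallback it borrows averages Month 3 to Month 6. Which quantity is reported could therefore be settled after the data are seen, in an open-label study.

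A related weakness is that random patient plus AR(1) forces equal variance at both visits. That affects a Month 6 standard error.

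**Working it through.** The plan gives no figure to reproduce on this point; SAP 5.1 bases the sample size on feasibility.

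**1. Parameter count.** Let b be the patient variance, s the residual variance and r the AR(1) correlation. The marginal covariance of visits i and j is V_ij = b + s·r^|i-j|. With two visits:

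- variance at each visit: v = b + s
- covariance: c = b + r·s

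These are two equations in three unknowns. Numerically, the Jacobian from (b, s, r) to the distinct elements of V has rank 2 for two visits and rank 3 for three, four or six visits.

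**2. The ridge.** For any r, s = (v - c)/(1 - r) and b = v - s reproduce the same V, provided b is not negative. To illustrate, two-visit data for 10 patients were simulated with b = 200, s = 150, r = 0.4 and means of -30% and -40% (all assumed). REML gave v = 638.4 and c = 506.1, so v - c = 132.3:

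| r | s | b | -2 REML log-likelihood | Month 6 LS mean (SE) | Average (SE) |
|---|---|---|---|---|---|
| 0 | 132.3 | 506.1 | 123.402486 | -40.64 (7.99) | -34.51 (7.56) |
| 0.4 | 220.6 | 417.9 | 123.402486 | -40.64 (7.99) | -34.51 (7.56) |
| 0.6 | 330.9 | 307.6 | 123.402486 | -40.64 (7.99) | -34.51 (7.56) |

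The standard errors depend only on v and c: √(638.4/10) = 7.99 and √((638.4 + 506.1)/20) = 7.56. From four starting points the optimiser ended at b between 2.8 and 521 and r between -0.12 and 0.79, each time with one Hessian eigenvalue equal to zero to numerical accuracy. Runs with 6 and 14 patients showed the same pattern.

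**3. Convergence.** In 150 simulated two-visit data sets of 10 patients, a general-purpose optimiser reported convergence in 150. With six visits it did so in 145 of 150. The SAS procedure the SAP would use was not tested.

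**4. AUC fallback read literally.** The average is (Month 3 + Month 6)/2. With assumed means:

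| Month 3 | Month 6 | Average | Shift from Month 6 |
|---|---|---|---|
| -30% | -30% | -30% | 0 points |
| -30% | -35% | -32.5% | 2.5 points |
| -30% | -40% | -35% | 5 points |
| -20% | -40% | -30% | 10 points |

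**5. Equal-variance constraint at Month 6.** With complete data the constrained model uses the mean of the two visit variances. With an assumed SD ratio of 1.5, that mean is (1 + 1.5²)/2 = 1.625.

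- Month 6 the more variable: √(1.625/2.25) = 0.85, so the standard error is 15% too small.
- Month 3 the more variable: √(1.625/1) = 1.27, so it is 27% too large.

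**The case against.** The strongest reply is that nothing reported for 24-hour urine changes. The quantity is the two-visit average, and with complete data the identifiable two-parameter version of the model gives the same LS mean and standard error as the fallback ANCOVA on patient averages. The equal-variance constraint then has no effect either. This stands. Missing visits could alter it, by an amount not quantified here.

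A reader might infer four stronger things that the documents and the checks do not support:

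- **That the estimates or degrees of freedom are arbitrary.** LS means and standard errors are constant along the ridge. Satterthwaite degrees of freedom were 8.27 at all four ridge points checked in one data set. Kenward-Roger was not tested, and the SAP names no method.
- **That the fallback will be triggered.** Failure is possible, but none occurred in the 150 two-visit fits.
- **That the AUC model certainly has three parameters.** SAP 7.3.1 states no covariance. Every MMRM that the SAP does specify is random patient plus AR(1), and the borrowed fallback is tied to an AR(1) fit, so the inference is reasonable; it remains an inference. The equal-variance figures depend on it too. They arise from the constraint, so an identifiable AR(1) or compound-symmetry model would give the same figures.
- **That the fallback must change the AUC quantity.** The SAP calls for a similar approach, and an ANCOVA of the Month 6 value could satisfy that wording. The text leaves the choice open.

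These are also secondary endpoints without planned p-values, with by-visit descriptive summaries and patient listings alongside.

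**Conclusion.** The covariance for 24-hour urinary oxalate is over-parameterised as written: three parameters against two identifiable quantities. This is algebra and rests on no assumption beyond the two-visit schedule. (The extracted Protocol Table 1 appears to put the single collection under Month 4, possibly a reading artefact; the count is two either way.) AUC(0-24h) and AUC(4-24h) have the same fault if the model specified elsewhere in the SAP is meant.

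The harm is to the specification. The variance split is arbitrary, and a singular-Hessian fit has no assigned status. For AUC only, the literal fallback could move the reported result by 0 to 10 percentage points under the assumed means. For urine the fallback keeps the Month 3 to Month 6 average. The 15% and 27% errors in the Month 6 AUC standard error depend on the assumed 1.5-fold SD ratio and on the inferred model.

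Plasma oxalate, including the primary endpoint, and the spot oxalate:creatinine ratio are scheduled monthly from Month 1 to Month 6 and are not affected. The point merits a SAP correction and casts no doubt on the primary analysis.

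**What to change.** For endpoints with two post-baseline visits (24-hour urinary oxalate, AUC(0-24h), AUC(4-24h)):

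1. Drop the random patient term and name one identifiable structure. The preferred choice is an unstructured 2×2 covariance with a stated small-sample degrees-of-freedom method. Its three parameters are all estimable and it removes the equal-variance constraint. AR(1) or compound symmetry alone is the simpler option and leaves the converged estimates and standard errors as they are.
2. State the AUC covariance explicitly in SAP 7.3.1.
3. State that a Hessian that is not positive definite counts as non-convergence.
4. State that the AUC fallback is an ANCOVA of the Month 6 value.

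Leave the monthly-visit endpoints unchanged.

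The cost is a few SAP sentences, with no new data or patients. The unstructured choice does have a price: somewhat fewer effective degrees of freedom at about 6 patients per cohort. In 60 simulated complete data sets of six patients, its standard error for the two-visit average ranged from 0.91 to 1.72 times the ANCOVA value, although the average cost was close to nil.

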7.3.3. Quality of Life (QoL)

The KDQOL-36 Burden of Kidney Disease and Effect of Kidney Disease on Daily Life subscales will be collected for adult patients to assess kidney disease specific measures and PedsQL Total score will be collected for pediatric patients to further assess quality of life. In both instruments, values range from 0 to 100 and lower scores indicate a worse self-reported QoL. Descriptive statistics will be generated for each instrument. Additionally, SF-12 Physical Component Summary (PCS) and Mental Component Summary (MCS) will be summarized for patients aged 18 or above.

CBI

CBI

CBI

[REDACTED]

7.3.5. Pharmacokinetics

Please see Section 7.5 for Pharmacokinetic analysis plan.

7.4. Exploratory Efficacy Analysis

Efficacy exploratory endpoints will be analyzed using the Full Analysis Set during the Primary Analysis Period and the Long-term Extension Period unless otherwise noted.

Exploratory endpoints will be analyzed and reported with by-patient listings and by-patient figures of actual values, change from baseline and percent change (where appropriate per endpoint) at each visit (scheduled and unscheduled visits). Tabular summaries using descriptive statistics (mean, standard error, median, min, max) will be reported. For binary endpoints, the number and percentages of patients in each category will be displayed at each visit.

7.4.1. Change from Baseline in Cardiac Systemic Oxalosis at Month 6

The change from baseline in Cardiac systemic oxalosis at Month 6 will be assessed by tabulating the number of patients with abnormal LVEF, GLS, or E/e' at baseline who improve by 5% in LVEF, 2% in GLS, and/or 2% in E/e' respectively in at least one of these measures at Month 6 and by assessing the mean change from baseline in these individual measures at Month 6 for all patients in FAS.

7.4.2. Growth Parameters (z-scores) and Change in Developmental Milestones

Change in growth parameters (z-scores) from baseline over time and changes in developmental milestones over time will be summarized descriptively.

The achievement of developmental milestones over time is assessed using Vineland Adaptive Behavior Scales for each scheduled visit for patients <6 years of age at consent. Composite scores for developmental milestones are collected and summarized using Vineland Adaptive Behavior Scales, second version (Vineland-II). Vineland-II consists of 5 domains each with subdomains. The adaptive levels associated with the domain and subdomain composite scores will be categorized and shift tables will be generated, details in Section 10.2. Vineland-II scores of each domain, subdomain, and the adaptive levels will also be presented in by-patient listing.

7.4.3. Quality of Life (QoL)

The change in QoL as assessed by EQ-5D-Y and PedsQL (individual subscales of the generic and ESRD modules, and ESRD module total score) for patients ≥ 2 to <18 years of age at consent. The change in QoL as assessed by EQ-5D-5L and KDQoL Symptoms and Problems of Kidney Disease subscale in patients ≥ 18 years of age at consent.

Descriptive statistics for the actual and change from baseline will be presented for each scheduled visit.

7.4.4. Patient and Caregiver Resource Use

The patient caregiver resource use (eg, work/school attendance, visits to doctor/hospital) will be summarized descriptively for each scheduled visit.

7.4.5. Patient and Caregiver Experience

The patient caregiver experience will be summarized descriptively for each scheduled visit.

7.4.6. Anti-drug Antibody

Analysis of ADA is included in Section [7.7](#).

7.4.7. Percent and Absolute Change from Baseline in Urinary and Plasma Glycolate

The percent and absolute change from baseline in plasma glycolate and spot urinary glycolate: creatinine ratio will each be summarized at each scheduled assessment.

7.5. Pharmacokinetic Analysis

Pharmacokinetic analyses will be conducted using noncompartmental methods. PK parameters will be calculated using a validated version of Phoenix® WinNonlin.

7.6. Safety Analyses

Primary safety analysis is a descriptive summary of frequency of AEs using the Safety Analysis Set. Other safety parameters will include vital signs, ECGs, clinical laboratory assessments and physical exams.

Safety analysis will be conducted for the Primary Analysis Period and extension period.

7.6.1. Adverse Events

The primary safety parameter is treatment emergent AEs. A treatment emergent AE will be defined as an AE that occurs or worsens on/after the first dose date/time of lumasiran through 84 days after the last dose. In addition, any AE that worsened in intensity or was subsequently considered related to lumasiran will be considered treatment emergent.

AEs will be classified using the Medical Dictionary for Regulatory Activities (MedDRA Version 21.1 or later) and displayed in tables using System Organ Class (SOC) and Preferred Terms (PT). All treatment emergent AEs hereafter will be referred to as AEs in this document.

An overview table of AEs will be generated. The overview table will include the number and percentage of patients in categories such as, but not limited to:

- At least 1 AE
 - At least 1 drug related AE
- At least 1 severe AE

- At least 1 drug related severe AE
- At least 1 Serious Adverse Event (SAE)
 - At least 1 drug related SAE
- At least 1 AE leading to treatment discontinuation
 - At least 1 drug related AE leading to treatment discontinuation
- At least 1 AE leading to study withdrawal
 - At least 1 drug related AE leading to study withdrawal
- At least 1 AE leading to treatment interruption
 - At least 1 drug related AE leading to treatment interruption
- Death

Tabulations by System Organ Class (SOC) and Preferred Term (PT) displaying the number of patients (percentage) and total events will be produced for the following tables:

- All AEs
- Severe AEs
- AEs by Maximum Severity
- AEs related to treatment
- AEs related to treatment by Maximum Severity
- All SAEs
- SAEs related to treatment
- AEs leading to treatment discontinuation
- AEs leading to treatment interruption
- AEs leading to study withdrawal

Tabulations by PT in decreasing order of frequency will be generated for the following tables:

- All AEs
- All SAEs
- AEs related to treatment
- SAEs related to treatment

There will also be an All AE table generated displaying rates of AEs adjusted for exposure-time.

Patients who report multiple occurrences of the same AE (preferred term) will be classified according to the most severe occurrence or most related.

Separate listings will be provided for deaths, SAEs, and AEs leading to discontinuation of study drug, withdrawal of study drug and/or dose interruption. By-patient AE listings will be provided.

Additional summaries will also be generated:

Injection Site Reactions [ISRs]: AEs mapping to the High-Level Term (HLT)= “Injection Site Reactions” using MedDRA dictionary will be included in the summary. Frequency (percentages) of ISRs by HLT and PT will be generated. A separate listing will be generated to display all patients who reported ISRs. In addition, a table of the number of patients with at least 1 ISR, total number of doses (any dose split into multiple injections will be considered 1 dose), total number of doses with ISRs and corresponding % of injections with ISR with the most common signs and symptoms reported due to ISRs will be generated.

Hepatic AEs, including Liver Function Test (LFT) abnormalities: Analysis of hepatic AEs will include AEs mapping to the Standardized MedDRA Query (SMQ) Drug-related hepatic disorders - comprehensive search (includes all narrow and broad terms). Frequency (percentages) of Drug-related hepatic disorders will be summarized by SOC and PT. A separate listing will be generated of all patients reporting these events.

